### **Risks related to TAF-FTC PrEP**

Study medication risks and side effects related to TAF-based PrEP include: occurring in a minority of individuals taking PrEP - gastrointestinal intolerance, such as nausea, diarrhea or vomiting, flatulence typically during the first month after PrEP initiation; rare but serious side effects of lactic acidosis/ severe hepatomegaly with steatosis, renal impairment, including cases of acute renal failure and Fanconi's syndrome (renal tubular injury with severe hypophosphatemia), increase in bone metabolism leading to osteopenia, and hypersensitivity reaction. Because TAF achieves lower blood concentrations but higher concentrations in tissue after dosing, these risks are hypothesized to be lower compared FTC/TDF PrEP, the currently approved oral PrEP regimen.

### **Risks from vaginal biopsy**

Vaginal tissue biopsy is an invasive procedure and we have carefully considered the risk involved including some discomfort, pain and potential for bleeding and burden on cisgender women. Sampling vaginal tissue is important to fully characterize HIV protection in cisgender women since it is a tissue of relevance to the acquisition of HIV infection for cisgender women and will help to define early drug kinetics and how soon drugs accumulate in vaginal tissue from PrEP initiation until steady state. To minimize risks, we have carefully considered sampling schedule to minimize risk associated with this procedure and burden on cisgender women: Each participant will provide only one biopsy in a 4-week period by sampling unique cisgender women (i.e., for each planned tissue sampling visit different cisgender women will be sampled at day 4 and day 7). All participants will provide a vaginal tissue sample for week 4 and 8.

### **Social harm and stigma risks**

We have considered the risk of social harm related to both DOT study medication use and frequent clinic visits, including risks of depression/anxiety and disclosure and stigma. Our extensive experience with successful and safe longitudinal follow-up of cisgender women at risk mitigates some of this risk, and we will measure social harms and provide/refer services when harms are reported. Participants also may become embarrassed, worried, or anxious while completing surveys or interviews regarding sexual behavior and acceptability. Counseling will be provided by clinical study staff who have been trained in specific issues related to STI/HIV risk, PrEP, STI/HIV acquisition, and care of HIV infected cisgender women, including stigma, blame, methods to avoid transmission, and available support services.

### **Behavior disinhibition risks**

The potential for behavior disinhibition may exist as a result of PrEP and is an important outcome, especially given the potential for some participant to receive less than daily dosing of PrEP. This study is specifically recruiting cisgender women at low risk of HIV, which reduces this risk. Nevertheless, we will use brief standardized questionnaires, which we have used for prior studies in cisgender women to explore partner number, sexual frequency, and condom use over time.

### **Privacy and confidentiality risks**

Although study site will make every effort to protect participant privacy and confidentiality, it is possible that participants' involvement in the study could become known to others. For example, participants could be treated unfairly or discriminated against, or could have problems being accepted by their families

and/or communities. We have extensive experience with the strategies to minimize the potential for social harms in populations participating in HIV prevention studies.

### **Risks from other study procedures**

Blood for safety labs and study pharmacokinetic samples will be collected from each subject during the study period. Blood will be collected from an arm vein and by fingerstick. Risks of blood draws include pain when the needle or lancet pierces the skin, bruising, and/or infection. The blood volumes are well below the maximal volumes set for blood donations and clinical research in 18 weeks. Approximately 100 strands of hair will be cut from the back portion of the scalp on multiple occasions. This could leave a noticeable spot from where the hair was cut.

## **8.5 Approaches to Minimize Risks**

### **Protection of risks related to non-daily PrEP dosing**

We have carefully considered the risk associated with using non-daily dosing for PrEP (i.e., 2 or 4 doses per week) in non-pregnant cisgender women and the potential for behavior disinhibition as a result of PrEP is an important outcome. We will make all efforts to enroll only healthy cisgender women volunteers deemed at low risk for HIV. We will rely on Kenya national guidelines as well as published HIV risk scores (Voice risk) to guide identification of cisgender women who may be at elevated risk of HIV to guide recruitment into this study –those found to be at elevated risk for HIV will be immediately linked for PrEP and other prevention services here at the Thika site or at the participants' clinic of choice. Each visit will include risk-reduction counseling for all cisgender women. All participants in this study will have an HIV test at baseline and then every 4 weeks, with immediate discontinuation of PrEP in case of HIV seroconversion.

### **Protection against risks related to TAF-FTC PrEP**

All participants will have HIV testing, creatinine testing, hepatitis B, and urine pregnancy testing at baseline. Only cisgender women with creatinine clearance >60 mL/min and uninfected with hepatitis B will be enrolled. Testing of volunteers for HBV-infection is conducted to protect subjects from HBV-associated hepatitis flares when study drugs are withdrawn. Breastfeeding will not be allowed to prevent risks to nursing infants. We will exclude subjects who have serious underlying illnesses such as cancer and heart disease. All participants will be counseled about potential side effects at enrollment and at each follow up visit, and they will be reminded that the side effects are self-limiting within 1-2 weeks. Subjects will be followed with clinical laboratories at entry and 10 weeks (serum creatinine, complete hematology, monthly pregnancy urine test) and more frequently with interviews to assess tolerability and safety over the course of the study, including during directly observed dosing. Participants will be tested for HIV infection at any point during the study as needed, and prior to and at the final visits of the dosing periods.

The most likely risks associated with TAF-FTC in HIV-negative persons appear to be reversible gastrointestinal complaints, headache, and/or weight decrease. These side effects are most likely mild and reversible. There is a remote risk of serious side effects including renal injury, lactic acidosis with hepatomegaly and steatosis, bone pathology, hypophosphatemia, hepatitis, pancreatitis, and there are possible side effects not listed here, or possible unforeseen long-term complications. We believe the risk of these serious side effects is remote given the rarity of the events during long-term treatment and PrEP in previous studies. We have designed the inclusion and exclusion criteria to exclude subjects who might be at higher risk of these toxicities. We have also designed a monitoring strategy for early detection of side effects and for quick study drug discontinuation, if needed, to protect subjects.

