## 2.5 Study Design

This is an open-label, randomized, three-arm, directly observed therapy, pharmacokinetic study of TAF-FTC PrEP among low-risk HIV-uninfected non-pregnant cisgender women. HIV-uninfected non-pregnant cisgender women at low risk for HIV will be randomly assigned to 1 of 3 dosing frequencies of DOT TAF-FTC PrEP (**Figure 3**): 2, 4, or 7 doses per week to help differentiate poor and modest from perfect adherence (**Figure 3**).

Enrollment will continue until 54 non-pregnant evaluable participants (i.e., participant with completed data on dosing and PK samples) are enrolled.

- **Group #1: "7 doses per week or Perfect Adherence arm"** — cisgender women will receive a single tablet of co-formulated 25 mg TAF/ 200mg FTC once daily (7 doses per week).
- **Group #2: "4 doses per week or Moderate Adherence arm"** — cisgender women will receive a single tablet of co-formulated 25 mg TAF/ 200mg FTC tablet on Monday, Tuesday, Thursday, Friday.
- **Group #3: "2 doses per week or Poor Adherence arm"** — cisgender women will receive a single tablet of co-formulated 25 mg TAF/ 200mg FTC tablet on Monday and Tuesday

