## **5.2 Enrollment and Follow up Procedures**

Up to 54 evaluable HIV uninfected participants will be enrolled and followed up for 18 weeks: 10 weeks with DOT PrEP and up to 8 weeks for post drug kinetics sampling, with one visit at one week following dose cessation and an additional visit to occur between weeks 12 to 18. Enrollment must occur within 30 days of screening. An eligible participant who is unable to schedule a study entry visit within the 30-day screening window must be re-screened prior to entry into the study. All enrolments will be scheduled on specific days to avoid confusion in implementing the proposed dosing and sampling scheme. An adverse event questionnaire and medical and medication review will be conducted at each visit from study entry (enrollment) through week 10. Safety labs and vitals can be ordered as needed at any visit.

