### **5.2.1 Dosing schedule and assessment of compliance**

The design of the study is guided by the ~17-day half-life of TFV-DP in DBS, and includes 10 weeks of dosing to achieve approximately 90% of steady-state, weekly sampling at convenience times (i.e., rather than troughs), and three dosing groups (2, 4, and 7 doses per week) to demonstrate dose-proportionality. All cisgender women will have 10 weeks of DOT PrEP to establish steady state in DBS and WB. We have chosen a dosing frequency scheme for non-daily doses to directly replicate the STRAND DOT study schedule based on the ~17-day half-life of TFV-DP in DBS: The 2 doses per week will be taken on Monday and Tuesday, and the 4 doses per week on Monday, Tuesday, Thursday, and Friday. This schedule will permit simultaneous evaluation of concentrations derived from intermittent and day-by-day dosing. The operationalization of specific days for dose taking can be adjusted prior to study start while maintaining the randomized adherence patterns (frequency of dosing taking) to permit efficient study operations and to minimize the burden on study participants. This is possible due to the long half-life of TFV-DP and planned sampling at steady state. Therefore, any chosen days would be appropriate.

All doses will be witnessed, as described above, in person by a study personnel in either a private room at the Thika clinic or at another predetermined location to maximize convenience for the participant. On dosing visits, the participant will take the dose by mouth and study personnel will ensure the tablet is swallowed by asking the participant to show that their mouth is empty. Flexible clinic scheduling will be available to promote high rates of follow-up and compliance and to minimize participants' burden. Where dosing cannot be witnessed in person, dosing will be witnessed over video via WhatsApp, Zoom, FaceTime, Skype, or other video-streaming device that is agreed upon by the participant and study

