## **6.3 Adverse Event Definition and Reporting**

An adverse event (AE) is defined as any untoward medical occurrence in a clinical research participant administered an investigational product and which does not necessarily have a causal relationship with the study product (TAF/FTC). As such, an AE can be an unfavorable or unintended sign (including an abnormal laboratory finding, for example), symptom or disease temporally associated with the use of an investigational product, whether or not considered related to the product.

Study participants will be provided a 24-hour telephone number and contact information and instructed to contact the study clinician to report any AEs they may experience. For life-threatening events, they will also be instructed to seek immediate emergency care. Where feasible and medically appropriate, participants will be encouraged to seek evaluation where the study clinician is based, and to request that the clinician be contacted upon their arrival. With appropriate permission of the participant, whenever possible, records from all non-study medical providers related to AEs will be obtained and required data elements will be recorded on study CRFs. All participants reporting an AE will be followed clinically, until the AE resolves (i.e., returns to baseline) or stabilizes.

Study site staff will document AEs in source documents and the appropriate e-CRF. Grade 1 and higher clinical AEs, Grade 2 and higher laboratory AEs, and any AE (clinical or laboratory) that leads to a study product hold (temporary or permanent) that are reported by or observed in enrolled (defined as after randomization has occurred) study participants will be captured on AE e-CRFs regardless of their severity and presumed relationship to the study product. AE severity will be graded per the DAIDS Table for Grading Adult and Pediatric Adverse Events, Version 2.1 corrected, July 2017.

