## 7.3 Data Analysis

### 7.3.1 Primary outcomes

**Primary outcome 1:** The goal is to describe the frequency of adverse events, including emergent HIV infection during the study period. We will conduct a descriptive analysis for meeting PrEP157 eligibility among participants. The distribution of demographics and graded adverse events will characterize by overall and study arms and proportions will be compared between study arms using chi-square statistics.

**Primary outcome 2:** The goal is to quantify the effect of dose on steady state TFV-DP in DBS and PBMC based on an incomplete block design.  $C_{ss}$  (drug concentration at steady state) will likely require a normalizing log transform, such that geometric means and CIs will be reported. Dose proportionality will be assessed using the power model (on the natural log scale)  $\ln(Y_{ijk}) = \mu + S_i + P_j + \beta \log(D_k) + \varepsilon_{ijk}$  (Eqn. 1). Where  $Y_{ijk}$  is the response,  $C_{ss}$ , for the  $k$ th dose ( $k=2, 4, 7$  doses/week),  $j$ th period ( $j=1,2$ ),  $i$ th subject ( $i=1, \dots, 45$ );  $\mu$  is the overall mean,  $S_i$  is a random subject effect,  $P_j$  is the period effect and  $\varepsilon_{ijk}$  is random error. Dose proportionality dictates that  $\beta=1$  for dose-dependent parameters and we will assume dose proportionality if the 90% CI is contained within the limits (0.8, 1.25). The SAS mixed procedure will be utilized for model (Eqn 1), again assuming a random subject effect. Although we do not anticipate a period effect, our design allows us to test this effect. For the primary analysis, we assume no effect of 'non-daily dosing' regimens; although this will be examined in a secondary analysis. If dose proportionality is not shown, we will examine proportionality separately for each of the "non-daily dosing" dosing regimens. If dose proportionality is still not demonstrated when adherence regimens are examined separately we will consider dose as a categorical predictor.

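### AEs may also be elicited at dosing contacts, which number about 70, 40 or 20 by arm, yet the between-arm AE comparison does not separate events by where they were elicited

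*Combined protocol and SAP*

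**What the plan says.** **Common schedule.** Section 5.2: "An adverse event questionnaire and medical and medication review will be conducted at each visit from study entry (enrollment) through week 10". Table 2 marks AE assessment at clinic visits 1 to 12, with no split by arm.

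**Possible extra elicitation.** Section 8.5, under protection against risks related to TAF-FTC PrEP, says that participants will be followed with laboratory tests at entry and week 10, and "more frequently with interviews to assess tolerability and safety over the course of the study, including during directly observed dosing".

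**Dosing contacts.** The daily arm takes one tablet every day (section 2.5). For the other arms, section 5.2.1 says: "The 2 doses per week will be taken on Monday and Tuesday, and the 4 doses per week on Monday, Tuesday, Thursday, and Friday". It also says "All cisgender women will have 10 weeks of DOT PrEP" and "All doses will be witnessed, as described above, in person by a study personnel", with video as the fallback.

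**Recording and analysis.** Section 6.3 captures "Grade 1 and higher clinical AEs, Grade 2 and higher laboratory AEs", whether reported by or observed in participants. In section 7.3.1, primary outcome 1 describes graded AEs overall and by arm, and "proportions will be compared between study arms using chi-square statistics". It neither restricts nor stratifies by how an event came to light. Section 7.5 confirms that the trial is open-label.

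**The concern.** Randomisation normally protects a comparison of AE proportions. Here the assignment itself sets how often staff meet each woman. If staff ask about symptoms at those meetings, women on more doses per week are asked more often. Section 8.5 expects mostly mild, reversible gastrointestinal complaints and headache, and such events are the most likely to go unreported unless someone asks. Women and staff also know the dosing frequency.

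The resulting bias points the same way as real dose-related toxicity. Safety is the first primary objective, so a higher AE proportion in the daily arm could be read as a dose effect when part of it reflects more frequent questioning.

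**Working it through.** The documents give no alpha, power or expected rate for the AE comparison, so there is no planned figure to reproduce.

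**1. Contacts per arm** (sections 2.5 and 5.2.1)
- Dosing contacts over 10 weeks: 7 × 10 = 70, 4 × 10 = 40, 2 × 10 = 20, a ratio of 3.5 : 2 : 1.
- Scheduled AE assessments (Table 2): 12 : 12 : 12.
- Distinct contact days: the entry visit is already a dosing day, so at most 11 common visits add a day. This gives 70, 40 to 51, and 20 to 31. The daily arm has between 70/31 = 2.3 and 70/20 = 3.5 times the contact days of the 2/week arm.

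**2. Recorded events with no drug effect.** The documents give no capture rates, so these are assumptions: the weekly visit captures a minor event with probability w = 0.4 to 0.6, and each dosing contact that week with a further probability q = 0.05 to 0.20. Then

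capture = 1 − (1 − w)(1 − q)^n, with n = 2, 4, 7.

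| w, q | 2/week | 4/week | 7/week | ratio 7:2 |
|---|---|---|---|---|
| 0.6, 0.05 (smallest) | 0.639 | 0.674 | 0.721 | 1.13 |
| 0.5, 0.10 (central) | 0.595 | 0.672 | 0.761 | 1.28 |
| 0.4, 0.16 (largest) | 0.577 | 0.701 | 0.823 | 1.43 |

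**3. What the chi-square would see.** The natural unit for a proportion is a woman with at least one AE. Assume minor events are Poisson with mean m = 1 to 3 per woman. Then P(at least one recorded) = 1 − exp(−m × capture). At the central capture values, with 18 women per arm and an assumed two-sided 0.05:

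| m | 2/week | 4/week | 7/week | ratio 7:2 | false-positive rate |
|---|---|---|---|---|---|
| 1 | 45% | 49% | 53% | 1.19 | 6.6% |
| 2 | 70% | 74% | 78% | 1.12 | 7.5% |
| 3 | 83% | 87% | 90% | 1.08 | 6.0% |

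Rejection rates are by exact enumeration of the three binomial counts. At w = 0.6, q = 0.05 the rate is about 5%. At w = 0.4, q = 0.16 to 0.20 it is 8% to 10%.

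**4. Sensitivity to recall.** A separate simulation assumed 0.5 to 2 mild episodes per woman, each lasting 1 to 2 days, and a much higher capture of 0.5 to 0.9 per dosing contact. With no true arm difference, the false-positive rate depends on the share of episodes that the common questionnaire recovers:

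| Recovered at common visits | false-positive rate |
|---|---|
| 0% | 0.16–0.70 |
| 25% | 0.09–0.32 |
| 50% | 0.06–0.11 |
| 75% | 0.05–0.07 |
| 100% | 0.04–0.06 |

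The direction is always more recorded AEs with more doses per week. With equal capture in all arms, as a common-visit comparison aims for, the rate is about nominal.

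**The case against.** **The premise rests on one clause.** The wording in section 8.5 may mean the DOT phase, not each dosing contact. Sections 5.2 and 5.2.2 and Table 2 place AE assessment at clinic visits common to all arms. Section 5.2.1 describes the dosing contact as a swallow check, a dosing log and meal information, with no AE interview. This stands: a reader might infer that AEs are certainly elicited at every dose, and the documents do not establish that. They leave it open. Even on the narrower reading, section 6.3 takes in anything reported to or observed by staff, and section 4.9 has staff record vomiting immediately after dosing.

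**Other channels are equal.** Besides the 12 assessments, every woman has a calendar for unsolicited AEs (section 3.6) and a 24-hour telephone number (section 6.3). These give a common floor and may recover most events.

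**The comparison is modest.** The stated goal is descriptive, with no safety hypothesis or power. This lowers the stakes, but the chi-square comparison is still planned under a primary outcome.

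**The illustration is simplified.** It makes each event detectable at every dosing contact in the week, and does not allow for a dosing contact coinciding with the clinic visit. At the same q, a one-day event would give a smaller ratio.

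**Restricting the source has a cost.** Events seen only at dosing, such as immediate vomiting, may be truly dose-related. Dropping them could hide real signal, which is why a common-visit comparison should accompany the all-source one and not replace it.

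**Conclusion.** The point holds as a risk of unequal ascertainment that the plan leaves open. The contact counts and the absence of any separation by source in section 7.3.1 are certain. Whether AE questions are asked at dosing contacts is not. The effect would fall mainly on mild, transient clinical AEs.

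The size is unknown and turns on recall at the common visits. Under the assumed capture rates, recorded events are 13% to 43% higher in the 7/week than in the 2/week arm. The false-positive rate on women with any AE is about 5% to 10% if each has 1 to 3 minor events on average. It would be larger only if the common questionnaire missed most mild episodes while dosing contacts caught many.

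A reader might infer that the AE comparison cannot be interpreted at all. The documents and the figures do not support that. What follows is narrower: an arm difference in all-source AEs could not, by itself, be separated from unequal questioning. That is worth correcting before data collection, because the source of an AE is hard to reconstruct later.

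**What to change.** 1. In sections 5.2 and 8.5, state whether AE questions are asked at dosing contacts.
2. Add an AE e-CRF field for where each event was first elicited: common clinic visit, dosing contact, or unscheduled. The protocol mentions no such field; the e-CRF is not among the documents, so check whether one exists.
3. At the common visits, use the same questionnaire in all arms with recall since the last clinic visit, and include events already mentioned at dosing.
4. In section 7.3.1, report the between-arm comparison on common-visit AEs alongside the all-source comparison. Attribute an arm difference to dose only if it also appears in the common-visit analysis.

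**Cost.** One e-CRF field, one line on the questionnaire and short additions to the text. Every AE is still recorded for safety oversight. The common-visit comparison will omit some events seen only at dosing, possibly including true dose-related ones, so all-source AEs must still be shown by arm. Differential recall may not be fully removed, because women prompted at dosing may remember more at the common visit.

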## 2.4 Secondary Objectives

- 1) To define the expected concentrations and dose-proportionally for TFV-DP in PBMC and vaginal tissue
- 2) To examine relationships among drug concentrations in plasma, WB, DBS, and PBMC.
- 3) To determine the influence of biological variables (e.g., HCT, age, weight, sex, metabolites from metabolomics, and genetic variability in drug transporter/clearance proteins) on drug concentrations.
- 4) To compare drug concentrations in DBS from fingerstick versus drug concentrations in DBS transferred from blood tubes.

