#### **5.1 Screening Procedures**

**Screening for COVID-19 symptoms and protection measures:** We will follow the standard of care of the Kenya Ministry of Health, KEMRI, and WHO guidelines on the COVID-19 virus. Participants will be informed about practicing good hand hygiene, masking, good respiratory hygiene, and maintaining social distancing. Staff will adhere to social procedures including maintaining a six foot distance and wearing masks. Unvaccinated participants and staff will be screened for COVID-19-related symptoms when they arrive at the clinic using a checklist to check for risk of COVID-19 exposure based on symptoms or contacts. Any person that comes to the clinic with symptoms consistent with COVID-19 that include 1 or more of fever, cough (dry or productive), dyspnea, or myalgias will be isolated. Participants will be educated about the Ministry of Health specified measures for seeking healthcare during this time. Referral

mechanisms to local public health facilities are in place. Finally, the clinical site will maintain a register of all visitors and participants who enter the study site, to support usual care contact tracing efforts where necessary.

At the screening visit a qualified study clinician will perform a history and physical exam for each participant. A complete medication history will be obtained including all drug allergies, immunization history, prescription, over the counter, and herbal treatments. Vital signs will include height, weight, blood pressure, pulse, respiratory rate and temperature. The following procedures will be conducted:

- Informed consent
- Safety Labs: Complete blood count (CBC, specifically hematocrit and hemoglobin), HBV surface antigen, serum creatinine)
- HIV antibody (rapid test or blood)
- Urine pregnancy test
- Medical, medication, vaccine history
- Physical exam

A screening test(s) may be repeated within the 30-day screening window. A participant who is unable to schedule a study entry visit within the 30-day screening window must be re-screened prior to entry into the study. Participants who have not been immunized for HBV will be offered vaccination, as per standard of care. An HBV Antibody test may be ordered for participants who are unsure of their vaccination history.

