### **5.2.3 Clinical Evaluations/Procedures**

Scheduled protocol visits and procedures are outlined in Table 5. At the screening visit a qualified study clinician will perform a history and physical for each participant. A complete medication history will be obtained including all drug allergies, immunization history, prescription, over the counter, herbal treatments, contraception use history. Vital signs will include height, weight, blood pressure, pulse, respiratory rate and temperature.

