##### ***Blood***

A blood sample will be obtained at protocol specified visits to process plasma, whole blood, DBS, and PBMCs. On a given study day blood collection, up to 21mL of blood for study bloodwork will be drawn with no planned timing relationship with dosing. The blood will be collected from an arm vein by trained clinic staff according to study site policies and procedures.

The schedule of protocol visits and procedures are outlined in Table 2.

Table 2: Schedule of protocol visit schedule and procedures.

Timeline (weeks)	Screening	Entry	DOT PrEP Period (weeks)											Post DOT Period	
			W1		W2	W3	W4	W5	W6	W7	W8	W9	W10	W11	W12-18
			Day 4	Day 7											
Clinic Visits #		1	2	3	4	5	6	7	8	9	10	11	12	13	14
Procedure															
Informed consent	x														
Medical, sexual, contraception, antenatal history review, vaccine history	x	x	x	x	x	x	x	x	x	x	x	x	x		
Physical exam a	x														
Dispense back up PrEP medication e		x													
Issue medical calendar		x													
AE assessment		x	x	x	x	x	x	x	x	x	x	x	x		
Safety Labs a,c	x	[x]											x		
Urine βHCG a	x	[x]						x				x			
HBS Ag	x														
HIV-1 rapid test a	x	[x]						x			x				
Hair collection							x			x		x			x
hDNA	x		x												
Study Bloodwork d (WB, plasma, DBS, PBMC)*PBMC is collected bi-weekly		x	x	x	x	x	x	x	x	x	x	x	x	x	x
Vaginal tissue f			x	x			x					x			
Vaginal swab		x	x	x			x				x		x		
DBS by fingerstick			x	x			x				x		x		
Study Urine d		x	x	x	x	x	x	x	x	x	x	x	x	x	x
Concomitant Medication Review	x	x	x	x	x	x	x	x	x	x	x	x	x		
STI testing (CT,GC, syphilis, HSV-2)		x											x		
DOT b		x	x	x	x	x	x	x	x	x	x	x	x		

[x] Indicated if screening occurred more 30 days before planned enrollment. The screen and entry visits must be ≤ 30 days apart.

a. Safety labs or vitals can be performed as needed at any time

b. DOT performed if applicable per randomization schedule

c. Protocol-specified safety labs include: CBC, HbAg, Creatinine clearance, in addition to monthly HIV testing and urine pregnancy tests.

d. Study Bloodwork: WB, DBS, PBMC, plasma and all available blood cell types; Study Urine: endogenous molecules such as nucleosides.

\*PBMC is collected bi-weekly (baseline, week 2, 4, 6, 8, 10)

e. Study medications will be dispensed as described

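### Weight decrease is named among the most likely drug risks, but weight is scheduled only at screening, so weight change on treatment is not measured systematically

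*Combined protocol and SAP*

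**What the plan says.** Section 8.5, under protection against risks related to TAF-FTC PrEP, says: "The most likely risks associated with TAF-FTC in HIV-negative persons appear to be reversible gastrointestinal complaints, headache, and/or weight decrease". It continues: "These side effects are most likely mild and reversible". That second sentence carries reference 45, which the reference list shows to be a TRUVADA (TDF/FTC) document. The paragraph closes with the claim: "We have also designed a monitoring strategy for early detection of side effects".

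Weight as a measurement appears in two places, both tied to screening. Section 5.1 says: "Vital signs will include height, weight, blood pressure, pulse, respiratory rate and temperature". Section 5.2.3 gives the same list after the sentence: "At the screening visit a qualified study clinician will perform a history and physical for each participant".

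After screening, vital signs are discretionary. Section 5.2 says: "Safety labs and vitals can be ordered as needed at any visit". Footnote a to Table 2 says: "Safety labs or vitals can be performed as needed at any time".

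For capture of events, section 5.2 plans an adverse event questionnaire at every visit from entry to week 10. Section 6.3 records clinical events from Grade 1 upward, whether reported or observed, and grades them by the DAIDS table. Section 7.3.1 (primary outcome 1) describes graded events overall and by arm and compares proportions between arms by chi-square.

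**The concern.** Gastrointestinal complaints and headache are felt, so a questionnaire suits them. Weight change is a difference between two measurements, and only one is planned. That one may precede the first dose by up to 30 days, so there is no scheduled weight at the start of treatment either.

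Two things are at stake. First, the protocol expects these effects to be mild, and mild weight loss is the kind that a complaint-driven system tends to miss. A finding of little or no weight decrease would then say little. Second, primary outcome 1 compares arms. Whether anyone weighs a woman after screening depends on what she says and what staff notice. Both know her arm, and the number of contacts differs by arm.

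**Working it through.** The plan states no figure on this point, so the check is a count over the schedule.

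**1. Scheduled weights.** The inputs are sections 5.1, 5.2.2 and 5.2.3 and Table 2.

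| Part of the schedule | Visits | Scheduled weights |
|---|---|---|
| Screening | 1 | 1 |
| Entry to week 10 (visits 1–12, all with an AE assessment in Table 2) | 12 | 0 |
| After dosing (visits 13–14) | 2 | 0 |
| Total | 15 | 1 |

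No list for visits 1 to 14 contains weight, vital signs or a physical examination. Table 2 has no row for weight or vital signs, and it marks the physical examination at screening only. Scheduled on-treatment changes available: 0 of 54 women.

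**2. Routes that remain.** Three are open:
- the participant reports weight loss at an AE questionnaire or interview;
- a clinician observes it;
- someone orders an as-needed weight and compares it with the screening value.

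All three depend on a prompt. None yields a value for every woman at a common time.

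**3. Opportunity by arm.** Section 8.5 includes directly observed dosing among the occasions for safety interviews, and section 5.2.1 has all doses witnessed over 10 weeks. Planned dosing contacts per woman are:
- 7 doses per week: 7 × 10 = 70
- 4 doses per week: 4 × 10 = 40
- 2 doses per week: 2 × 10 = 20

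The largest ratio is 70 / 20 = 3.5. This is an upper indication of unequal opportunity, not an estimate of bias. The 12 AE assessments at clinic visits are common to all arms, and some dosing contacts are by video.

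**4. The two risk statements side by side.** Section 8.4 lists the risks of TAF-based PrEP: gastrointestinal intolerance, lactic acidosis with hepatomegaly, renal impairment, bone effects and hypersensitivity. Weight is not on that list. Section 8.5 puts weight decrease among the three most likely risks, and the sentence that follows cites a TDF/FTC source. The documents do not say which statement is meant to govern monitoring.

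**The case against.** The strongest reply is that the protocol does not leave weight loss undetectable. Vital signs may be taken at any visit, and in Table 2 the footnote that allows this is attached to the physical examination row. A questionnaire runs through week 10, events observed by staff count, and a screening weight exists for comparison. This stands. A reader might infer that the primary safety outcome cannot detect or grade weight decrease, or that no comparison between arms is possible. The documents support neither inference. Whether grading needs a measured percentage change cannot be settled here, because the DAIDS criteria are cited but not reproduced.

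It can also be said that the effect is expected to be mild, that participants are told side effects settle within 1–2 weeks, and that 18 women per arm with no untreated group could not readily attribute weight change to drug. These points limit the importance of the gap. They also mean that weights at weeks 4 and 10 could miss an early, transient loss. They do not explain how the schedule delivers early detection of a risk that the protocol names.

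Two further inferences should be resisted:
- **Creatinine clearance.** A reader might argue that an old weight distorts the calculated clearance in section 6.8.4. The formula is not stated, section 3.1 speaks of estimated glomerular filtration rate, and the only follow-up creatinine in the visit lists is at week 10, the last scheduled dosing visit.
- **Covariates.** A reader might argue that a screening weight or BMI is too old for the adjusted analyses. A baseline value is an ordinary covariate, and nothing in the plan calls for weight that varies over time.

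**Conclusion.** The point holds as a gap between a stated risk and the measurement schedule. Weight change on treatment is not measured systematically: one scheduled weight in 15 visits, none at the 12 AE assessment visits, and no scheduled change for any of the 54 women. Capture through report, observation or discretion is possible. It is likely to under-count mild loss, and it may differ between arms.

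The schedule count comes directly from the documents. The under-counting is a judgement, resting on the protocol's own expectation that the effect is mild. The unequal capture is a possibility, resting on the open-label design and the 70, 40 and 20 dosing contacts; its size cannot be computed. The safety outcome is mainly descriptive and the pharmacokinetic objectives are untouched, so this is an inexpensive improvement rather than a threat to the trial.

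**What to change.** 1. Add weight to the section 5.2.2 visit lists and to Table 2 at entry (visit 1), as the baseline, and at existing on-treatment visits: at minimum week 10 (visit 12) and preferably also week 4 (visit 6).
2. Under primary outcome 1 in section 7.3.1, tabulate change in weight from entry by arm, as a descriptive summary beside the graded adverse events.
3. Reconcile the risk statement in section 8.5 with the TAF risk list in section 8.4. Say whether weight decrease is regarded as a TAF-FTC risk, and give a source that concerns TAF-FTC.

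The cost is a few minutes on the scale already used at screening and one eCRF field at each chosen visit, with no extra visit or sample. If the sponsor prefers not to add the measurement, section 8.5 should say that weight change is ascertained only by report, observation or as-needed weighing, and the early-detection claim should be limited to match.
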